5.7.4.3.2 Males

Male subjects must practice complete abstinence (NOTE: True abstinence is acceptable when this is in line with the preferred and usual lifestyle of the subject. Periodic abstinence [e.g., calendar, ovulation, symptothermal or post-ovulation methods] and withdrawal are not acceptable methods of contraception.) or agree to use a condom during sexual contact with a pregnant female or a FCBP while taking lenalidomide, during dose interruptions and for at least 28 days after the last dose of lenalidomide, even if he has undergone a successful vasectomy.

5.7.4.4 Pregnancy Precautions for Lenalidomide Use

5.7.4.4.1 Before Starting Lenalidomide

5.7.4.4.1.1 Females of Childbearing Potential

Females of childbearing potential must have two negative pregnancy tests (sensitivity of at least 25 mIU/mL) prior to starting lenalidomide. The first pregnancy test must be performed within 10 to 14 days prior to the start of lenalidomide and the second pregnancy test must be performed within 24 hours prior to the start of lenalidomide. The subject may not receive lenalidomide until the study doctor has verified that the results of these pregnancy tests are negative.

Females of childbearing potential must use two reliable forms of contraception simultaneously, or practice complete abstinence (True abstinence is acceptable when this is in line with the preferred and usual lifestyle of the subject. Periodic abstinence [e.g., calendar, ovulation, symptothermal or post-ovulation methods] and withdrawal are not acceptable methods of contraception.) from heterosexual contact for at least 28 days before starting lenalidomide.

5.7.4.4.1.2 Males

Male subjects must practice complete abstinence (NOTE: True abstinence is acceptable when this is in line with the preferred and usual lifestyle of the subject. Periodic abstinence [e.g., calendar, ovulation, symptothermal or post-ovulation methods] and withdrawal are not acceptable methods of contraception.) or agree to use a condom during sexual contact with a pregnant female or a FCBP while taking lenalidomide, during dose interruptions and for at least 28 days after the last dose of lenalidomide, even if he has undergone a successful vasectomy

5.7.4.4.2 During and After Study Participation

5.7.4.4.2.1 Female Subjects

- Females of childbearing potential with regular or no menstrual cycles must agree to have pregnancy tests weekly for the first 28 days of study participation and then every 28 days while taking lenalidomide, at study discontinuation, and at Day 28 following the last dose of lenalidomide.
- Females of childbearing potential with irregular menstrual cycles must agree to have pregnancy tests weekly for the first 28 days of study participation and then every 14 days while taking lenalidomide, at study discontinuation, and at Days 14 and 28 following the last dose of lenalidomide (or 120 days post discontinuation of pembrolizumab (Arm A).

- At each visit, the investigator must confirm with the FCBP that she is continuing to use two reliable methods of birth control if not committing to complete abstinence, or confirm commitment to complete abstinence.
- If a FCBP considers the need to change or to stop a method of contraception, the investigator must be notified immediately.
- Counseling about pregnancy precautions and the potential risks of fetal exposure must be conducted at a minimum of every 28 days.
- If pregnancy or a positive pregnancy test does occur in a subject, lenalidomide must be immediately discontinued.
- Pregnancy testing and counseling must be performed if a subject misses her period or if her pregnancy test or her menstrual bleeding is abnormal. Lenalidomide must be discontinued during this evaluation.
- Females must agree to abstain from breastfeeding while taking lenalidomide and for at least 28 days after the last dose of lenalidomide.

5.7.4.4.2.2 Male Subjects

- Must practice complete abstinence (True abstinence is acceptable when this is in line with the preferred and usual lifestyle of the subject. Periodic abstinence [e.g., calendar, ovulation, symptothermal or post-ovulation methods] and withdrawal are not acceptable methods of contraception.) or use a condom during sexual contact with a pregnant female or a FCBP while taking lenalidomide, during dose interruptions and for at least 28 days after the last dose of lenalidomide (or 120 post discontinuation of pembrolizumab (Arm A), even if he has undergone a successful vasectomy.
- Must not donate semen or sperm while receiving lenalidomide, during dose interruptions or for at least 28 days after the last dose of lenalidomide.
- Counseling about pregnancy precautions and the potential risks of fetal exposure must be conducted at a minimum of every 28 days.
- If pregnancy or a positive pregnancy test does occur in the partner of a male subject while taking lenalidomide, the investigator must be notified immediately.

5.7.4.4.2.3 Additional Precautions

- Subjects should be instructed to never give lenalidomide to another person.
- Subjects should be instructed to return any unused capsules to the study doctor.

- Subjects should not donate blood while receiving lenalidomide, during dose interruptions and for at least 28 days after the last dose of lenalidomide.
- No more than a 28-day lenalidomide supply may be dispensed with each cycle of lenalidomide.
- If a subject inadvertently becomes pregnant while on treatment with pembrolizumab, lenalidomide and low dose dexamethasone, the subject will immediately be removed from the study and the Sponsor should be notified by the site without delay within 24 hours.
- Study investigators from United States sites should report any suspected fetal exposure to lenalidomide to Celgene Corporation (at ^{PPD} [REDACTED]) and to FDA via the MedWatch Program (at ^{PPD} [REDACTED]).

5.8 Subject Withdrawal/Discontinuation Criteria

Subjects may withdraw consent at any time for any reason or be dropped from the trial at the discretion of the investigator should any untoward effect occur. In addition, a subject may be withdrawn by the investigator or the Sponsor if enrollment into the trial is inappropriate, the trial plan is violated, or for administrative and/or other safety reasons. Specific details regarding discontinuation or withdrawal procedures; including specific details regarding withdrawal from Future Biomedical Research, are provided in Section 7.1.4 – Other Procedures.

A subject must be discontinued from the trial for any of the following reasons:

- The subject or legal representative (such as a parent or legal guardian) withdraws consent.

A subject must be discontinued from treatment (but may continue to be monitored in the trial) for any of the following reasons:

- The subject or legal representative (such as a parent or legal guardian) withdraws consent for treatment but agrees to continue to participate in the regularly scheduled study activities.
- Documented disease progression as assessed by the investigator. (i.e., 2 consecutive assessments are needed for disease progression. Clinical deterioration will not be considered progression). Note: Subjects with documented disease progression may continue to receive trial treatment, at the discretion of the study investigator prior consultation with the Sponsor, if they meet the criteria outlined in Section 7.1.2.8.6.
- Unacceptable adverse experiences as described in Sections 5.2.1.2 and 5.6.1.
- Intercurrent illness that prevents further administration of treatment.

- The subject has a confirmed positive serum pregnancy test.
- Subjects who receive any non-protocol specified anti-myeloma therapy prior to documented progression will be discontinued from all study treatment (including lenalidomide and low dose dexamethasone); however, tumor assessments must continue at 4 week intervals until documented progression.
- Noncompliance with trial treatment or procedure requirements.
 - Subjects experiencing a > 12 weeks delay between pembrolizumab doses in the investigational arm (Arm A) or > 28 day delay for both lenalidomide and low dose dexamethasone in the control arm (Arm B) due to an adverse event(s) related to study treatment must be discontinued from treatment.
 - Subjects experiencing >28 days delays in all study drugs due medical/surgical events or logistical reasons unrelated to study therapy must be discontinued from treatment.

NOTE: For both groups, if either pembrolizumab, lenalidomide or low-dose dexamethasone is discontinued due to unacceptable toxicity, subjects can continue to receive study treatment with the remaining study drugs without discontinuing from study.

- The subject is lost to follow-up.
- Administrative reasons.

The End of Treatment and Follow-up visit procedures are listed in Section 6 (Flow Chart) and Section 7.1.5 (Visit Requirements). After the end of treatment, each subject will be followed for 30 days for AE monitoring (SAEs will be collected for 90 days after the end of treatment as described in Section 7.2.3.1). Subjects who discontinue for reasons other than progressive disease will have post-treatment follow-up for disease status until disease progression, initiating a non-study cancer treatment, withdrawing consent or becoming lost to follow-up. Prior to discontinuing patients from therapy, consult with Sponsor and submit the Treatment Termination & Disease Assessment Termination Form. After documented disease progression or the start of new antineoplastic therapy, each subject will be followed for overall survival until death, withdrawal of consent, or the end of the study, whichever occurs first.

5.9 Subject Replacement Strategy

A subject who discontinues from the trial will not be replaced.

5.10 Beginning and End of the Trial

The overall trial begins when the first subject signs the informed consent form. The overall trial ends when the last subject completes the last study-related phone-call or visit,

discontinues from the trial or is lost to follow-up (i.e. the subject is unable to be contacted by the investigator), or the Sponsor ends the trial, whichever occurs first.

5.11 Clinical Criteria for Early Trial Termination

Early trial termination will be the result of the criteria specified below:

1. Quality or quantity of data recording is inaccurate or incomplete,
2. Poor adherence to protocol and regulatory requirements,
3. Plans to modify or discontinue the development of the study drug pembrolizumab.
4. A request made by the U.S. Food and Drug Administration or other similar Health Authority due to safety concerns.

In the event of Sponsor decision to no longer supply study drug pembrolizumab, ample notification will be provided so that appropriate adjustments to subject treatment can be made.

6.0 TRIAL FLOW CHART

6.1 Trial Flow Chart

Trial Period:	Screening Phase	Treatment Cycles						End of Treatment		Post-treatment		
		Cycles 1-3 to be repeated beyond 3 cycles										
Treatment Cycle/Title: (28 days cycles)	Screening (Visit 1)	Cycle 1		Cycle 2		Cycle 3		Discon ^o	Post-Treatment Safety Follow-up	Efficacy Follow-up Visits	Survival Follow-up	
Cycle Day (visit day) (± 3 days after C1D1 unless otherwise specified)	(-28 to -1 days)	1 (+ 3 days)	22	1	15	1	8	At time of Discon	30 days post Discon	Every 4 weeks post Discon (± 7 days)	Every 12 weeks (± 7 days) or as directed by the Sponsor	
Administrative Procedures												
Informed Consent	X											
Informed Consent for Future Biomedical Research	X											
Inclusion/Exclusion Criteria	X											
Subject Identification Card	X											
Demographics and Medical History	X											
International Staging System (ISS)	X											
Prior and Concomitant Medication Review ^d	X	X	X	X	X	X	X	X	X			
Register REVLIMID REMS™ program (US ONLY) or country specific risk mitigation program	X											
Pregnancy Prevention Counseling ^l	X	X		X		X						
Obtain randomization number and study drug assignment using IVRS/IWRS	X											
Pembrolizumab Administration		See Section 6.1.1										
Lenalidomide Administration												
Dexamethasone Administration												
Post-study anticancer therapy status								X	X	X		
Survival Status ^p		↔							↔		X	
Clinical Procedures/Assessments												
Review Adverse Events ^d	X	X	X	X	X	X	X	X	X	X		
Full Physical Examination	X	X		X		X		X				
Directed Physical Examination (Arm A only)			X		X		X					
Vital Signs and Weight ^{a,d}	X	X	X	X	X	X	X	X				

Trial Period:	Screening Phase	Treatment Cycles						End of Treatment		Post-treatment	
		Cycles 1-3 to be repeated beyond 3 cycles									
Treatment Cycle/Title: (28 days cycles)	Screening (Visit 1)	Cycle 1		Cycle 2		Cycle 3		Discon ^o	Post-Treatment Safety Follow-up	Efficacy Follow-up Visits	Survival Follow-up
Cycle Day (visit day) (± 3 days after C1D1 unless otherwise specified)	(-28 to -1 days)	1 (+ 3 days)	22	1	15	1	8	At time of Discon	30 days post Discon	Every 4 weeks post Discon (± 7 days)	Every 12 weeks (± 7 days) or as directed by the Sponsor
12-Lead Electrocardiogram	X										
ECOG Performance Status	X	X		X		X		X			
Skeletal survey	X										
MRI or CT or PET/CT for extramedullary soft tissue plasmacytoma	X										
Disease Response Assessment by IMWG 2011 criteria [1] ⁿ		X ⁿ		X		X		X	X	X	
Laboratory Procedures/Assessments: analysis performed by local laboratory											
Pregnancy Test – Urine or Serum β-HCG ^b	X	X ^b		X		X		X	X		
Archival or new Bone Marrow Biopsy or Aspirate for disease characterization ^e	X										
Laboratory Procedures/Assessments: analysis performed by central laboratory											
PT/INR and aPTT	X ^e										
CBC with Differential ^{d,n}	X ^e	X ⁿ	X	X	X	X	X	X	X		
Comprehensive blood Chemistry Panel ^{d,n}	X ^e	X ⁿ	X	X	X	X	X	X	X		
LDH	X ^e					X		X	X		
Urinalysis	X ^e					X			X		
T3, (or FT3 per local standard), FT4 and TSH	X ^e					X			X		
Serum protein electrophoresis with M-protein quantitation	X	X		X		X		X	X	X ^f	
Quantitative Serum Immunoglobulin	X	X		X		X		X	X	X ^f	
Serum immunofixation	X	X		X		X		X	X	X ^f	
Serum free light chain assay	X	X		X		X		X	X	X ^f	
24 hr urine protein electrophoresis with M-protein quantitation	X	X		X		X		X	X	X ^f	
24 hr urine immunofixation	X	X		X		X		X	X	X ^f	
β2 microglobulin	X										
Archival or new Bone Marrow Biopsy or Aspirate	X										

Trial Period:	Screening Phase	Treatment Cycles						End of Treatment		Post-treatment	
		Cycles 1-3 to be repeated beyond 3 cycles									
Treatment Cycle/Title: (28 days cycles)	Screening (Visit 1)	Cycle 1		Cycle 2		Cycle 3		Discon ^o	Post-Treatment Safety Follow-up	Efficacy Follow-up Visits	Survival Follow-up
Cycle Day (visit day) (± 3 days after C1D1 unless otherwise specified)	(-28 to -1 days)	1 (+ 3 days)	22	1	15	1	8	At time of Discon	30 days post Discon	Every 4 weeks post Discon (± 7 days)	Every 12 weeks (± 7 days) or as directed by the Sponsor
for Minimal Residual Disease Characterization ^m											
Bone Marrow Aspirate for Bone Marrow Exploratory Sub-Study ^c	X			X				X			
Whole Blood for Correlative Studies (RNA/DNA) ^j		X		X				X			
Blood for biomarker studies (Plasma and serum)	X										
Anti-pembrolizumab Antibodies for the investigational arm (Arm A) only ^g		X	X		X				X		
Pharmacokinetics for the investigational arm (Arm A) only ^g		X	X		X				X		
Blood for Genetic analysis ^h		X									
Patient Reported Outcomes											
EuroQol EQ-5D ⁱ		X		X		X		X	X		
EORTC QLQ-C30 ⁱ		X		X		X		X	X		
EORTC QLQ-MY20 ⁱ		X		X		X		X	X		

- Investigational arm (Arm A) should have vital signs measurements on Day 1 of each cycle and on the day of pembrolizumab infusion before and immediately after each administration of the study drug. Weight measurement not required post infusion.
- For females of child bearing potential two negative pregnancy tests (sensitivity of at least 25mIU/ml) must be obtained within 10-14 days AND within 24 hours prior to C1D1 weekly during Cycle 1 and then monthly in women with regular menstrual cycles, or every 2 weeks in women with irregular menstrual cycles Refer to Section 7.1.5.2 Pregnancy Testing for additional details .
- Bone marrow analysis for all subjects at baseline will include bone marrow morphology, IHC and cytogenetics by standard FISH panel for disease status assessment at local institution. If FISH is not available, then do standard karyotyping. An archival or newly obtained sample may be used at Screening. For subjects who agree to participate in the optional biomarker sub-study, freshly obtained bone marrow aspirate sample may be collected at C1D1, C2D1 and at time of discontinuation.
 Note: If the subject signs the Future Biomedical Research (FBR) consent, any leftover tissues that would ordinarily be discarded at the end of the trial will be retained for FBR. A copy of the local pathology report, with subject information removed, should also be sent to the lab to accompany the biopsy specimen.
- Control arm (Arm B) only, measure CBC with differential, comprehensive blood chemistry panel, vital signs, review AEs, prior and concomitant medications, and perform a physical examination on Day 1 of each cycle. Subjects in Arm B only need 1 visit per month on Day 1 of each cycle. For subjects who discontinue pembrolizumab in Arm A, but continue on the study, subsequent visits are also only needed once per month.
- Laboratory safety tests for Screening are to be performed within 10 days prior to the first dose of trial treatment. Laboratory safety tests are not required to be repeated on Cycle 1

Trial Period:	Screening Phase	Treatment Cycles						End of Treatment		Post-treatment	
		Cycles 1-3 to be repeated beyond 3 cycles									
Treatment Cycle/Title: (28 days cycles)	Screening (Visit 1)	Cycle 1		Cycle 2		Cycle 3		Discon ^o	Post-Treatment Safety Follow-up	Efficacy Follow-up Visits	Survival Follow-up
Cycle Day (visit day) (± 3 days after C1D1 unless otherwise specified)	(-28 to -1 days)	1 (+ 3 days)	22	1	15	1	8	At time of Discon	30 days post Discon	Every 4 weeks post Discon (± 7 days)	Every 12 weeks (± 7 days) or as directed by the Sponsor

Day 1. See Section 7.1.3.1 for additional details regarding laboratory safety tests.

- f. Myeloma laboratory testing should be performed in the follow-up period for all subjects who discontinue study treatment for reasons other than disease progression.
- g. Pre-dose trough PK and anti-pembrolizumab antibody samples will be collected at C1D1, C1D22, C2D15, C5D15 and every 4 pembrolizumab infusions thereafter, and 30 days after discontinuation of study drug (or until the subject starts new anti-cancer therapy). Pharmacokinetic/anti-drug antibody (PK/ADA) samples may be used to conduct additional safety analysis, if needed.
- h. This sample should be drawn for planned analysis of the association between genetic variants in DNA and drug response. If there is either a documented law or regulation prohibiting collection, or if the IRB/IEC does not approve the collection of the sample for these purposes, then this sample will not be collected at that site. If the sample is collected, leftover extracted DNA will be stored for future biomedical research if the subject signs the FBR consent. If the planned genetic analysis is not approved, but FBR is approved and consent is given, this sample will be collected for the purpose of FBR.
- i. Patient reported outcomes (PROs) are assessed on day 1 of Cycle 1 (every 28-day cycle) through Cycle 4 and then every 3 cycles (i.e., Cycle 7, 10, 13, etc.) while the subject is receiving study treatment, at treatment discontinuation, and at 30 days post treatment discontinuation (post-treatment safety follow-up).
- j. Whole blood for correlative studies (RNA/DNA) should only be collected at C1D1, C2D1 and at discontinuation.
- k. Cycle 1 treatment must be administered within 3 calendar days of randomization number assignment in IVRS/IWRS, after ensuring subjects meet disease criteria through previous consultation with the Sponsor.
- l. The Lenalidomide Education and Counseling Guidance Document must be completed for all subjects and signed by a trained counselor prior to each dispensing of lenalidomide in accordance with the REVLIMID REMS™/country-specific risk mitigation program. A copy of this document must be maintained in the subject's records for each dispense for all countries/sites where lenalidomide is provided centrally by the Sponsor.
- m. All subjects in this study need to provide an archival or new bone marrow biopsy or fresh aspirate for minimal residual disease (MRD) characterization for central analysis at Screening, and fresh bone marrow biopsy or aspirate material at the time of achieving a Complete Response (CR), and at 6 months and 1 year after achieving a CR.
- n. Disease Response Assessment by IMWG 2011 criteria, CBC with Differential, and Comprehensive blood Chemistry Panel do not need to be performed on Cycle 1 Day 1.
- o. On 03-JUL-2017, the US FDA placed KN183, KN185 and cohort 1 of KN023 on clinical hold based on safety data from KN183 and KN185 presented to the DMC. The FDA determined that the risks of pembrolizumab plus pomalidomide or lenalidomide outweighed any potential benefit for patients with multiple myeloma. Based on this decision, the treatment phase of KN183 and KN185 is closed effective immediately. All subjects must stop study treatment, complete the Discontinuation Visit and move into the long-term safety and survival follow-up per protocol.
- p. After confirmed disease progression or start of new anti-myeloma therapy, the subject should be contacted approximately every 12 weeks to assess for survival status. Updated survival status may be requested by the Sponsor at any time during the course of the study. Upon Sponsor notification, all subjects who do not/will not have a scheduled study visit or study contact during the Sponsor-defined time period will be contacted for their survival status (excluding subjects who have previously recorded a death event in the collection tool).

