6.1.1 Trial Treatment Administration Schedule

Each Cycle = 28 Days (Cycles 1-3 to be repeated beyond 3 cycles)												
	Cycle 1				Cycle 2				Cycle 3			
Group A Investigational Arm^c												
Trial Treatment/ Cycle Day (± 3 days)	Days 1-7 (wk 1)	Days 8-14 (wk 2)	Days 15-21 (wk 3)	Days 22-28 (wk 4)	Days 1-7 (wk 1)	Days 8-14 (wk 2)	Days 15-21 (wk 3)	Days 22-28 (wk 4)	Days 1-7 (wk 1)	Days 8-14 (wk 2)	Days 15-21 (wk 3)	Days 22-28 (wk 4)
Pembrolizumab (Q3W) ^a	1			22			15				8	
Lenalidomide ^b	1 to 21				1 to 21				1 to 21			
Dexamethasone ^c	1	8	15	22	1	8	15	22	1	8	15	22
Pill count for Lenalidomide and Dexamethasone (Both groups) ^d	1				1				1			
Group B Control Arm^c												
Lenalidomide ^b	1 to 21				1 to 21				1 to 21			
Dexamethasone ^c	1	8	15	22	1	8	15	22	1	8	15	22

- Pembrolizumab will be administered as 200 mg every 21 days (3 weeks) as an IV infusion over 30 minutes.
- Lenalidomide will be administered as 25 mg PO, once daily on Days 1 to 21 of repeated 28-day cycles. Lenalidomide must be prescribed through and in compliance with the REVLIMID REMS™ program. Refer to local prescribing information.
- Low-dose dexamethasone will be administered as 40 mg PO, once daily on Days 1, 8, 15 and 22 of repeated 28-day cycles. A dexamethasone dose of 20 mg on Days 1, 8, 15 and 22 in subjects aged > 75 years is recommended. Refer to local prescribing information.
- Site should document drug accountability as per their institutional guidelines for both groups.
- On 03-JUL-2017, the US FDA placed KN183, KN185 and cohort 1 of KN023 on clinical hold based on safety data from KN183 and KN185 presented to the DMC. The FDA determined that the risks of pembrolizumab plus pomalidomide or lenalidomide outweighed any potential benefit for patients with multiple myeloma. Based on this decision, the treatment phase of KN183 and KN185 is closed effective immediately. All subjects must stop study treatment, complete the Discontinuation Visit and move into the long-term safety and survival follow-up per protocol.

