Laboratory safety tests for Screening should be performed within 10 days prior to the first dose of trial treatment. **Laboratory safety tests do not need to be repeated on Cycle 1 Day 1.** After Cycle 1, all laboratory tests will be performed by a central laboratory on Day 1 of each cycle and prior to pembrolizumab infusions for the investigational arm (Arm A). Specific laboratory tests may be performed locally, in parallel to central laboratory tests, at the discretion of the investigator, to ensure subject's safety prior to treatment. After Screening, pre-dose laboratory procedures can be conducted up to 72 hours prior to dosing. Results must be reviewed by the investigator or qualified designee and found to be acceptable prior to each dose of trial treatment.

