8.6.2 Statistical Methods for Safety Analyses

Safety and tolerability will be assessed by clinical review of all relevant parameters including adverse experiences (AEs), laboratory tests, vital signs, etc.

The analysis of safety results will follow a tiered approach (Table 17). The tiers differ with respect to the analyses that will be performed. Safety parameters or adverse experiences of special interest that are identified *a priori* constitute “Tier 1” safety endpoints that will be subject to inferential testing for statistical significance with p-values and 95% confidence intervals provided for between-group comparisons. Other safety parameters will be considered Tier 2 or Tier 3. Tier 2 parameters will be assessed via point estimates with 95%

confidence intervals provided for between-group comparisons; only point estimates by treatment group are provided for Tier 3 safety parameters. No formal treatment comparisons with p-values will be carried out.

Adverse experiences (specific terms as well as system organ class terms) and predefined limits of change in laboratory, vital signs, and ECG parameters will be classified as belonging to "Tier 2" or "Tier 3", based on the number of events observed. Membership in Tier 2 requires that at least 4 subjects in any treatment group exhibit the event; all other adverse experiences and predefined limits of change will belong to Tier 3.

The threshold of at least 4 events was chosen because the 95% confidence interval for the between-group difference in percent incidence will always include zero when treatment groups of equal size each have less than 4 events and thus would add little to the interpretation of potentially meaningful differences. Because many 95% confidence intervals may be provided without adjustment for multiplicity, the confidence intervals should be regarded as a helpful descriptive measure to be used in review, not a formal method for assessing the statistical significance of the between-group differences in adverse experiences and predefined limits of change.

Continuous measures such as changes from baseline in laboratory, vital signs, and ECG parameters will be considered Tier 3 safety parameters. Summary statistics for baseline, on-treatment, and change from baseline values will be provided by treatment group in table format.

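### While on pembrolizumab, Arm A has about twice Arm B's scheduled safety visits, so between-arm intervals for CBC, chemistry and vital-sign limits can show an Arm A excess from looking alone

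*Combined protocol and SAP*

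**What the plan says.** **Schedule.** Section 6.1 (Trial Flow Chart) sets a repeating three-cycle block with visits at C1D1, C1D22, C2D1, C2D15, C3D1 and C3D8. AE review, vital signs, CBC and chemistry are marked at each, except that "CBC with Differential, and Comprehensive blood Chemistry Panel do not need to be performed on Cycle 1 Day 1". The footnotes then limit the control arm: "Subjects in Arm B only need 1 visit per month on Day 1 of each cycle". The mid-cycle dates follow from the infusion interval in Section 6.1.1: "Pembrolizumab will be administered as 200 mg every 21 days (3 weeks) as an IV infusion over 30 minutes". Arm A vital signs are taken on Day 1 and "on the day of pembrolizumab infusion before and immediately after each administration of the study drug". Section 7.1.3.1 agrees on laboratory timing: "After Cycle 1, all laboratory tests will be performed by a central laboratory on Day 1 of each cycle and prior to pembrolizumab infusions" in Arm A. The flow chart also marks laboratory tests at C1D22, and the count below follows it. LDH, urinalysis and thyroid tests are marked once per block, on C3D1, for both arms. The extra visits end with pembrolizumab: "For subjects who discontinue pembrolizumab in Arm A, but continue on the study, subsequent visits are also only needed once per month".

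**Analysis.** Under Section 8.6.2, adverse experiences and "predefined limits of change in laboratory, vital signs, and ECG parameters will be classified as belonging to" Tier 2 or Tier 3. An item reaching at least 4 subjects in either arm is Tier 2 and gets a Miettinen-Nurminen 95% interval for the between-arm difference. The section does not say which visits supply the values. The one adjustment mentioned is an optional exposure-adjusted incidence, motivated by longer expected follow-up with pembrolizumab.

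**The concern.** Whether a subject ever crosses a laboratory or vital-sign limit depends on how often anyone looks. A brief, symptomless abnormality between two monthly visits goes unrecorded in Arm B, while the same abnormality in Arm A may meet an infusion-day draw. The plan allows for unequal follow-up time but not for unequal looking, which the protocol itself builds in. Because the extra visits stop when pembrolizumab stops, the intensity of detection also changes within Arm A.

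Treatment was closed on safety grounds, so the between-arm toxicity profile is a main remaining output. An excess of cytopenias, enzyme rises or vital-sign excursions that comes from the schedule would be read as an effect of adding pembrolizumab.

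**Working it through.** **1. The plan's own figure.** Section 8.6.2 says the interval always includes zero when equal arms each have fewer than 4 events. With 320 per arm (640 planned, 1:1), the score statistic at difference zero is z = (pA - pB) / sqrt[p(1-p)(2/320)(640/639)], where p is the pooled rate.
- 3 v 0: z = 1.735, interval includes zero.
- 4 v 0: z = 2.005, interval excludes zero.

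The threshold reproduces.

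**2. Scheduled contacts per 84 days on pembrolizumab.** Infusions fall on days 1, 22, 43 and 64; cycle Day 1s on days 1, 29 and 57. Arm A attends on the union (1, 22, 29, 43, 57, 64), Arm B on the second list.

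| Item | Arm A | Arm B |
|---|---|---|
| Visits and AE reviews | 6 | 3 |
| CBC/chemistry, first block (C1D1 exempt) | 5 | 2 |
| CBC/chemistry, later blocks | 6 | 3 |
| Vital-sign sets (4 infusion days x 2, plus 2 other Day 1s) | 10 | 3 |
| LDH, urinalysis, thyroid | 1 | 1 |

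**3. Timing.** Lenalidomide is given on Days 1-21. On the nominal schedule, every Arm B draw follows the seven days off. Arm A's extra draws fall on Day 22, Day 15 and Day 8, during or just after dosing. The documents give no time course for counts, so this is not modelled. If counts are lower during or just after dosing than after the rest week, it adds to the effect in the same direction.

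**4. Exposure adjustment.** Incidence density divides events by person-time. With equal person-time in both arms, 5.0% against 2.5% remains a ratio of 2 after the division, so the looks are not corrected.

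**5. Size, duration model.** Assumptions: no true difference, at most one episode per subject, uniform onset, detection only at scheduled visits. An episode of L days is detected with probability sum of min(gap, L) / 84. Gaps are 21, 7, 14, 14, 7, 21 days in Arm A and 28, 28, 28 in Arm B. For L = 14: Arm A 70/84 = 83%, Arm B 42/84 = 50%.

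Multiplying by the true incidence gives pA and pB. The approximate chance that the interval excludes zero against Arm A is Φ[(pA - pB - 1.96·SE0)/SE1], with SE0 pooled and SE1 unpooled. For L = 7 at 10% incidence: 5.0% v 2.5%, SE0 = 0.01502, SE1 = 0.01499, giving Φ(-0.296) = 38%.

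| L (days) | Detected A v B | Spurious points at 10% incidence | Chance | Spurious points at 40% incidence | Chance |
|---|---|---|---|---|---|
| 3 | 21% v 11% | 1.1 | 19% | 4.3 | 60% |
| 7 | 50% v 25% | 2.5 | 38% | 10.0 | 95% |
| 14 | 83% v 50% | 3.3 | 39% | 13.3 | 97% |
| 21 | 100% v 75% | 2.5 | 20% | 10.0 | 76% |
| 28 or more | 100% v 100% | 0 | 2.5% (nominal) | 0 | 2.5% (nominal) |

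**6. Size, independent-visit model.** If each visit is a fresh draw with detection chance q, the proportions are 1-(1-q)^6 and 1-(1-q)^3, with Miettinen-Nurminen intervals:
- q = 1%: 5.9% v 3.0%, interval -0.4 to 6.3 points.
- q = 2%: 11.4% v 5.9% (37/320 v 19/320), interval 1.3 to 10.2 points.
- q = 5%: 26.5% v 14.3% (85/320 v 46/320), interval 6.0 to 18.4 points.

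With the first-block laboratory counts of 5 and 2, q = 2% gives 9.6% v 4.0%. Correlation between visits pulls all of these towards zero.

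**The case against.** The other side has real force.

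- **AE reporting is continuous.** Section 7.2 requires all AEs from randomization to 30 days after treatment in both arms, so a monthly visit covers the interval since the last one. Sections 7.1 and 7.1.2.3 allow unscheduled assessment, and Table 5 recommends weekly CBC in either arm after a lenalidomide interruption for low counts. Arm B's actual laboratory frequency may exceed the schedule. This narrows the gap and confines it to findings with no symptoms.
- **Section 8.6.2 is not explicit.** It neither lists the limits nor says which visits count, and Table 17 has no Tier 2 row for laboratory or vital-sign limits. The text does place such limits in Tier 2 or 3, so the exposure exists, but using all visits is a natural reading, not a stated rule.
- **The intervals are descriptive.** There are no Tier 1 events and no safety p-values. That limits the consequence, but a descriptive interval that reflects the schedule still misleads.
- **Restricting the comparison to Day 1 has its own bias.** It drops real mid-cycle Arm A toxicity in a trial stopped for harm. This stands as a reason not to replace the all-visit comparison.

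A reader might infer that the Tier 2 comparisons as a whole will show spurious toxicity, or that the signal behind the clinical hold came from the schedule. The documents support neither. Deaths, SAEs, symptomatic Grade 3-5 AEs and discontinuations due to AEs depend little on visit count, and the risk named in the document history is an imbalance of deaths.

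**Conclusion.** The concern holds in limited form. While subjects are on pembrolizumab, the scheduled looks are about 2:1 for visits, CBC and chemistry and about 10:3 for vital-sign sets, and nothing in Section 8.6.2 corrects for this. Between-arm intervals for CBC, chemistry and vital-sign limits can therefore show an Arm A excess without any drug effect, as can the incidence of transient low-grade AEs found by those tests. Time to first Grade 3-5 AE is also exposed, since earlier looks can give earlier recorded onset.

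The size is not known. In the duration model it runs from zero (abnormalities lasting 28 days or more) to 3.3 points at 10% incidence and 13.3 points at 40%. Incidence, duration and per-visit detection chance are all assumptions, and 320 per arm is the planned number. Disease assessment is every 28 days in both arms, so PFS is not touched by this asymmetry. This is a cheap improvement to the safety tables, not a challenge to the safety conclusion.

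**What to change.** In Section 8.6.2 or the supplemental SAP:

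1. Keep the all-visit comparison.
2. Beside it, report a prespecified between-arm comparison of CBC, chemistry and vital-sign limits of change restricted to scheduled Day 1-of-cycle values: pre-infusion vital signs only, and laboratory values from C2D1 onward.
3. Do not apply the filter to AEs. The fields in Table 14 do not record how an event was detected. Instead, note that visit-detected low-grade AEs and time to first Grade 3-5 AE are open to ascertainment bias.

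Both arms already have the Day 1 data, and Sections 8.0 and 8.6.2 leave room for the change. The cost is wording and some extra programming. The Day 1 comparison omits real mid-cycle Arm A events; these remain in the all-visit comparison, so the two should be read together.
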